## Intervention Fidelity

Approximately 20% of sessions will be reviewed for fidelity purposes. Specifically, weekly sessions will be reviewed by any study member, other than the therapist. The randomization scheme is already determined and is located on the share drive along with the fidelity worksheets. If a reviewer is randomly assigned their own session, the reviewer will trade with the reviewer who comes after them, taking their next assigned session to review. A score of 80% or greater is required to pass. Once completed, the reviewer will score the interviewer and record the score and their initials in the randomization spreadsheet. Completed fidelity worksheets will be stored in the Fidelity folder located in room L107B file cabinet C. **Feedback should be provided to the therapist about important points that are missed.**

### Forms:

Fidelity Control Worksheet → P:\[name]-Lab\NRT Sampling\Manuals\Control  
Fidelity Intervention Worksheet → P:\[name]-Lab\NRT Sampling\Manuals\Sampling Intervention\Treatment A, B, C, or D

## Therapy Protocol

### Week 1 – Week 5

**Participants should work with the same staff member for the 5 weekly counseling sessions.**

#### Intervention Group A

##### Week 1

1. Check to see if any information on participant's contact sheet needs to be updated.
2. Administer the CO test. Refer to the CO directions under the "CO Monitor" section on Page 8 of this manual. Record the CO level in REDCap.
  - If the CO level is 3 or below, you need to administer a urine cotinine test to confirm that the participant is using nicotine products.
3. Gather either the 21 mg patch or the 14 mg patch and give it to the participant. **Patch dosage is based on number of cigarettes smoked determined at Baseline appointment. Be sure to write down the time that the patch is placed on their arm. Ideally, the participant should have the patch on for 30 minutes before the intervention begins.**
4. Gather either the 4mg gum or 2mg gum and give it to the participant. **Gum mg is based on how soon the participant smokes a cigarette after waking determined at Baseline**

**appointment). Wait to give the gum to the participant until the session is being recorded.**

5. Have the participant fill out all of the questionnaires related to the session in REDCap, **except the Credibility Expectancies Questionnaire, the SECOND Minnesota Nicotine Withdrawal Scale and the SECOND Questionnaire of Smoking Urges.**
6. While the participant is filling out the questionnaires on REDCap, have REDCap open on the desktop and double check for participant entry errors as they progress through the questionnaires.
7. Tell the client that you are about to start the recording for the session. Explain that “this is a manualized intervention; therefore it will not feel like traditional therapy. We will be working from a manual and will adhere to the manual content, exclusively.”
8. Turn on the recording and **state your name, the date, and the time that you are starting the therapy. Do your best not to say the participant’s name while being recorded.**
9. Give the participant the assigned client Intervention workbook and tell them to follow along as you go through your Therapist Intervention Manual. Let them know that the counseling could take up to 30 minutes and **they are urged to write down information in their workbooks.**
10. When appropriate, pause the audio recording and have the participant fill out the following:
  - **The second Minnesota Nicotine Withdrawal Scale**
  - **The second Questionnaire of Smoking Urges**
    - **Based on the participant’s response to the Minnesota Nicotine Withdrawal Scale and the Questionnaire of Smoking Urges, graph the before and after scores in their workbook.**
11. Un-pause the audio recording and continue the intervention by going over the participant’s before and after scores for the Minnesota Nicotine Withdrawal Scale and Questionnaire of Smoking Urges.
12. Go over the Tobacco Use and NRT Use calendars.
13. Provide them with the copies of the calendars (in their folder) to keep in their pocket/wallet for use when they do not have their manual with them.
14. After the therapy, ask the participant if they have any questions. If they do not, tell them you are ending the recording.
15. Schedule the next appointment for the following week (preferably the same day of the week and the same morning time). **Once you have it scheduled, make sure the appointment is placed on your UABMC calendar, desk calendar, and recorded in the REDCap Calendar application.**
16. Instruct the participant to **bring the calendars and workbook back so they can be reviewed next session.**
17. Give the participant 6 patches. The 6 patches and the patch they are currently wearing (total of 7) will last through to the next appointment.
18. Give the participant one package of gum. The pack of gum will last through to the next appointment. **Be sure to emphasize they are not to use the gum on the morning of the next appointment.**
19. Have the participant sign for the medication in the medication sign-out log.

20. Mark in the Medication Inventory Excel sheet how many of the patches and gum packages you have given out so that we maintain a running total of prescriptions we have on hand.
21. Remind the participant of the instructions on how to use the patches and gum and let them know they can reference their workbook if they forget. Give the participant the instructions sheet.
22. Compensate the participant on their Greenphire ClinCard.
23. Give the participant an appointment card. **Be sure to remind the participant to try and refrain from smoking the night before the appointment and not to use a patch or gum on the morning of the appointment. Also, remind them to bring all used and unused patches, patch packets, and gum packages back to the next appointment.**
24. Upload the session recording to Box.com (MOP, pg. 14) and complete the Audio Recording Length form in REDCap.

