## Control Group

### Week 1

1. Check to see if any information on participant's contact sheet needs to be updated.
2. Administer the CO test. Refer to the CO directions under the "CO Monitor" section on **Page 8** of this manual. Record the CO.
  - If the CO is 3 or below, you need to administer a urine cotinine test to confirm that the participant is using nicotine products.
3. Have the participant fill out all of the questionnaires related to the Session in REDCap, **except the SECOND Minnesota Nicotine Withdrawal scale, and the SECOND Questionnaire of Smoking Urges.**
4. While the participant is filling out the questionnaires on REDCap, have REDCap open on the desktop and double check for participant entry errors as they progress through the questionnaires.
5. Tell the client that you are about to start the recording for their session. Explain that "this is a manualized intervention; therefore it will not feel like traditional therapy. We will be working from a manual and will adhere to the manual content, exclusively."

6. Turn on the recording and state your name, the date, and the time that you are starting the therapy. Do your best not to say the participant's name while being recorded.
7. Give the participant the assigned client Control workbook and tell them to follow along as you go through your therapist control manual. Remind them that the counseling could take up to 30 minutes and they are urged to write down information in their workbooks.
8. **Make sure that you have gone over the Tobacco Use calendar before you finish the recording.** Provide them with copies of the calendar to keep in their pocket/wallet for use when they do not have their manual. Ask that they bring back the calendar and workbook to each visit.
9. After the therapy ask the participant if they have any questions. If they do not, tell them you are ending the recording.
10. Have the participant complete the remaining session measures (Credibility Expectancies Questionnaire, second Minnesota Nicotine Withdrawal Scale, and second Questionnaire of Smoking Urges).
11. Schedule the next appointment for the following week (preferably the same day of the week and same time). Once you have it scheduled, make sure the appointment is placed in the [name] Lab Google Calendar.
12. Compensate the participant on their Greenphire ClinCard.
13. Give the participant an appointment card.

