Intervention. In vivo Group. Participants in the intervention group will receive In vivo experience with four different forms of short acting NRT combined with patch and counseling focused on their experience of using NRT, including positive experiences, side effects and smoking cessation expectancies. For each session, participants will be instructed to arrive to session wearing the nicotine patch and to have gone as long as possible without smoking. The rationale for instructing patch use from the beginning is to promote the use of combination NRT as the expectation. Further, instructing participants to go as long as possible without smoking is to demonstrate the additive effect of short acting NRT for relieving cravings and withdrawal effects. Prior to each session and receipt of the short acting NRT, participants will complete the brief withdrawal (Minnesota Nicotine Withdrawal Scale [MNWS]) and craving (Questionnaire of Smoking Urges; QSU) measures; see Table 1 for a brief description. Participants will repeat these assessments at the end of their session. All sessions (In vivo or SC) will be approximately 30 minutes and will be conducted individually by research assistants (RAs) trained to use the In vivo manual and who are not tobacco treatment specialists to increase real-world application and dissemination of this approach (see In vivo manual in Appendix A).

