Session 1: At the end of the Baseline assessment (described below), In vivo participants will be given one nicotine patch and instructed to place it on their upper arm the day of their next appointment. If they arrive without the patch, they will immediately have a patch placed on their upper arm. They will then complete the assessment measures to allow the nicotine patch to demonstrate initial medication effects. The peak effects of nicotine patch occurs at 3.8 hours; however, initial detection of the drug occurs at 11.8 minutes⁵⁵. Thus, participants will be wearing the patch for at least 30 minutes of assessment or longer which should be sufficient to experience at least some of the effects of the patch for relieving withdrawal. Our pilot work demonstrated that In vivo participants experienced reduced withdrawal and craving within 30 minutes of administration. After assessment, the first few minutes of the intervention will focus on their in vivo experience of wearing the nicotine patch and will query previous experiences with the patch. We will solicit both positive (e.g., “the patch helps with cravings”) as well as negative perceptions (e.g., “it makes my arm itch”) of the patch. Participants will discuss any side effects they experience with using the nicotine patch in session. Next, participants will be given one of four short-acting forms of NRT (gum, lozenge, inhaler, nasal spray; counterbalanced across participants by session). Thus some participants may receive gum first, while others will receive inhaler, lozenge, or nasal spray. This will wash out any primacy or recency effects of NRT across participants for product selection. The gum, lozenge and inhaler demonstrate initial effects for relief of withdrawal around 5 minutes and peak effects after about 15 minutes, while the nasal spray occurs more rapidly and more closely mimics the relief from smoking⁵⁶⁻⁵⁷. Thus, the delivery of nicotine in these short-acting products should be fast enough for participants to experience the effects of the medication on withdrawal and craving symptoms during session, as we noted with gum in our previous pilot study. Safety and efficacy results specific to both the patch and the specific short-acting NRT administered will be reviewed with the participant. They will also discuss their expectancies for the effectiveness of these products for cessation. Participants will be given a week supply of nicotine patches and whichever short-acting product they were randomized to receive first to use

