NRT Adherence	X	X	X	X	X	X	X	X	X	

Note: BL=Baseline Assessment; S=session; WK=week; M=month; PS=Product Selection; ¹All participants will complete these surveys twice (at the beginning and end of session) during sessions 1-4.

Randomization. We anticipate enrolling 10 pre-pilot participants in 3 months and 80 participants in 20 months and, based on our previous study with this population, expect to retain at least 70% through the one month follow-up point. Randomization will occur after completion of the initial screening and assessment.

Primary Outcomes. Feasibility and acceptability will be measured through high study retention (70%) and recruitment (recruitment of all participants within 24 months) in our groups. Additional items of acceptability include high scores on treatment satisfaction and credibility/expectancies that are equal or higher to the SC

group. Medication adherence is a third primary outcome with expected differences between our groups. Adherence is notoriously difficult to determine. Self-reported adherence is not always reliable, particularly during treatment studies where there is a demand characteristic to report the desired targeted behavior⁷³⁻⁷⁴ (e.g., adherence to NRT). The behavioral methods described under the assessment section represent the best available self-report tools for determining NRT adherence (e.g., TLFB report, returning used NRT patches and used product blister packs/packaging). Adherence will be defined by self-report using the TLFB and verified through returned patches and packaging. Good adherence is defined by taking greater than 80% of doses of medication at each time point. We have used these techniques in previous studies with low income populations with good compliance for use of TLFB verified by return of NRT materials⁷⁵.

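### The second craving and withdrawal scales are taken before counselling ends in the In vivo groups but after the session in Control at Weeks 1-4, although the SAP sets end of session for everyone

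*Protocol*

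**What the plan says.** **SAP.** In the In vivo Group paragraph under Intervention, participants complete the MNWS and QSU before the session and before the short-acting product. Then: "Participants will repeat these assessments at the end of their session". The note to Table 2 applies this to both arms; all "participants will complete these surveys twice (at the beginning and end of session) during sessions 1-4". The MNWS and QSU entries in Table 1 likewise place the two readings before and after the session.

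**Protocol, In vivo.** In Therapy Protocol, Intervention Group A, Week 1, step 10 reads "When appropriate, pause the audio recording and have the participant fill out the following" and lists the second MNWS and second QSU. Staff graph the before and after scores, and step 11 begins "Un-pause the audio recording and continue the intervention by going over the" two sets of scores. Calendar review and closing questions follow. The same sequence stands in the Week 1-4 lists of Groups A to D. The Week 5 lists also use the pause, with product selection after it.

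**Protocol, Control.** At Week 1, calendar review comes first (step 8). Step 9 is "After the therapy ask the participant if they have any questions. If they do not, tell them you are ending the recording". Only then comes step 10: "Have the participant complete the remaining session measures (Credibility Expectancies Questionnaire, second Minnesota Nicotine Withdrawal Scale, and second Questionnaire of Smoking Urges". Weeks 2, 3 and 4 follow the same order. At Week 5, Control moves to the pause procedure.

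**The concern.** Decreases in withdrawal and craving are among the mechanisms the SAP proposes for better adherence (end of Preliminary Studies). In the Aim 3 analysis text, the SAP's main interest for these factors is whether In vivo shows decreases in withdrawal and craving relative to standard care. Taking the scales twice in one sitting makes sense mainly as a way to see within-session change. The earlier pilot described in the SAP reported that contrast between arms.

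For the contrast to speak to the product, the second reading should sit at the same point of the session in both arms. If it does not, the arms also differ in how long the session has run, what has been covered, and which questionnaire has just been filled in. An observed difference could then be credited to in-session NRT when part of it comes from when the question was asked.

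**Working it through.** The plan gives no figure for these scales, so there is none to reproduce. The check is a side-by-side reading, a range for the timing gap, and one labelled illustration.

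**1. Position of the second scales, Weeks 1-4**

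| | In vivo, Groups A-D | Control | SAP |
|---|---|---|---|
| Place in session | Recording paused, session still open | After questions and end of recording | End of session, all participants |
| Moment defined | No | Yes, by step order | Yes |
| Calendar review | After the reading | Before the reading | Not stated |
| Score feedback | Directly after the reading | None listed | Not stated |
| Other questionnaire alongside | None | Credibility questionnaire, listed first | Not stated |

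Control Weeks 1-4 fit the SAP. The In vivo lists do not, because the intervention is resumed after the reading.

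**2. Possible size of the timing gap.** Sessions last about 30 minutes (SAP); the Protocol says up to 30. If counselling runs 30 minutes and the In vivo pause falls at minute m, the In vivo reading is about 30 − m minutes before the end of counselling:

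- m = 15: 30 − 15 = 15 minutes
- m = 20: 30 − 20 = 10 minutes
- m = 25: 30 − 25 = 5 minutes

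The values of m are assumptions; no document gives one. The SAP states that "The gum, lozenge and inhaler demonstrate initial effects for relief of withdrawal around 5 minutes and peak effects after about 15 minutes", so onset to peak spans about 15 − 5 = 10 minutes. A gap of 5 to 15 minutes is of that order. The relevant clock, however, starts at product use. In Session 1 the product follows the patch discussion, and in Sessions 2-4 it follows review of the past week, so time since product is not time since the start of recording.

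**3. What is recorded.** Staff write down the patch time, speak the start time on the recording, and enter the recording length. No step records the time of the second scales. They are REDCap survey forms, so time stamps may exist, but the documents do not say so.

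**4. Reach.** With full attendance, 80 participants × 4 sessions = 320 before-after pairs for each scale. Only analyses that use the second reading are touched. The SAP specifies paired t-tests across time without saying which pair: before against after within a session, or visit against visit.

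**5. Illustration only.** Suppose there is no true difference between arms and the timing artefact is d standard deviations of the change score. Assume 1:1 allocation, two-sided alpha 0.05 and a normal approximation:

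rejection rate = Φ(d/SE − 1.96) + Φ(−d/SE − 1.96), with SE = √(2/n).

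The 80 randomised give n = 40 per arm (SE = 0.224). The SAP's 70% retention gives 0.7 × 40 = 28 per arm (SE = 0.267).

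| Assumed d | n = 40 per arm | n = 28 per arm |
|---|---|---|
| 0.1 | 7.3% | 6.6% |
| 0.2 | 14.5% | 11.6% |
| 0.3 | 26.9% | 20.2% |

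The values of d are invented to show sensitivity. Nothing in the documents supports one of them, or a direction.

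**The case against.** The strongest reply is that the difference may be small and may not enter any planned analysis. The parts of it are as follows.

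- **The therapist manual is not among the documents and may fix the moment.** This stands. A fixed moment would still come before score review and calendar work, so it would not match Control or the SAP.
- **The pause may fall near the end.** This stands; at minute 25 the gap is about 5 minutes. The content before the reading would still differ, since Control has done calendar review and closing questions and may just have completed another questionnaire.
- **Within-session change is never named as the analysed variable.** This stands and limits the reach. Comparing the first scales from visit to visit is untouched.
- **The arms are meant to differ, because only In vivo uses NRT in session.** True. In vivo participants are also asked not to smoke beforehand, while Control has no special instructions for the first session, so starting levels may differ as well. Aligning the timing does not make the contrast a pure product effect. It removes one avoidable component.
- **The switch of method in Control at Week 5 matters little.** Agreed. The SAP asks for two readings only in Sessions 1-4, and In vivo Week 5 lists no new short-acting product before the second scales.

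**Conclusion.** The inconsistency is established from the text. The In vivo lists conflict with the SAP's end-of-session rule, and at Weeks 1-4 the second MNWS and QSU are not taken at the same point in the two arms. Any between-arm comparison of within-session change in craving or withdrawal at those weeks mixes the product effect with timing and prior session content. The size and direction of the distortion cannot be determined; the figures in the illustration depend wholly on assumed artefacts.

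This should be corrected, but it concerns a mechanism measure in a pilot. Feasibility, acceptability and adherence do not use the second scales.

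Three stronger readings are tempting and are not supported:

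- **That therapists choose the moment to show the product at its best.** The documents leave the moment undefined. They do not say who sets it or why, and the therapist manual may do so.
- **That the In vivo reading is 10 to 15 minutes early.** That follows only from assuming a pause at minute 15 to 20.
- **That every between-arm comparison of craving and withdrawal is compromised.** Only those using the second reading are.

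**What to change.** - In both arms at Weeks 1-4, and at Week 5 if the second scales are kept there, give the second MNWS and QSU at one common point: when the manual counselling content ends, before score feedback, calendar review or any other questionnaire.
- In the In vivo lists, replace the open-ended instruction with that point. In the Control Weeks 1-4 lists, move the step to the same point, ahead of calendar review and the credibility questionnaire. Control Week 5 already pauses the recording, so a pause is workable; its calendar step would need the same reordering.
- State the same point in the SAP's In vivo Group paragraph, the Table 1 entries for the two scales and the Table 2 note.
- Record the clock time of the second scales and, in In vivo, of in-session short-acting product use, or use REDCap time stamps if available. A fixed minute from the start of recording would not serve: it does not fix time since product use, and a short session could end before it.
- If data are already collected, report the timing difference and caveat the Weeks 1-4 within-session contrast.

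The cost is a short pause in Control sessions and a small edit to the manuals and the SAP text, with no new forms or visits. If the change is made during enrolment, note its date, because it alters the method part-way through.

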## **Week 2**

1. Check to see if any information on participant's contact sheet needs to be updated.
2. Administer the CO test. Refer to the CO directions under the "CO Monitor" section on **Page 8** of this manual. Record the CO level in REDCap.
  - If the CO level is 3 or below, you need to administer a urine cotinine test to confirm that the participant is using nicotine products.
3. Collect the participant's Tobacco Use and NRT Use calendars and enter the data for the previous week into the appropriate SPSS database, then return the calendars to the participant.
4. Collect the used nicotine patches and gum packages and dispose of them after reviewing the calendars. Any unused patches/gum packages can be given back to the participant.
5. Gather either the 21 mg patch or the 14 mg patch and give it to the participant. **Patch dosage is based on number of cigarettes smoked determined at Baseline appointment. Be sure to write down the time that the patch is placed on their arm. Ideally, the participant should have the patch on for 30 minutes before the intervention begins.**
6. Gather the inhaler box and give it to the participant to use. **Wait to give the inhaler to the participant until the session is being recorded.**
7. Have the participant fill out all of the questionnaires related to the session in REDCap, **except the SECOND Minnesota Nicotine Withdrawal Scale and the SECOND Questionnaire of Smoking Urges.**
8. While the participant is filling out the questionnaires on REDCap, have REDCap open on the desktop and double check for participant entry errors as they progress through the questionnaires.
9. Tell the client that you are about to start the recording for the session. Explain that "this is a manualized intervention; therefore it will not feel like traditional therapy. We will be working from a manual and will adhere to the manual content, exclusively."
10. Turn on the recording and **state your name, the date, and the time that you are starting the therapy. Do your best not to say the participant's name while being recorded.**

11. Tell the participant to follow along in their client Intervention workbook as you go through your Therapist Intervention manual. Let them know that the counseling could take up to 30 minutes and **they are urged to write down information in their workbooks.**
12. When appropriate, pause the audio recording and have the participant fill out the following:
  - **The second Minnesota Nicotine Withdrawal Scale**
  - **The second Questionnaire of Smoking Urges**
    - **Based on the participant's response to the Minnesota Nicotine Withdrawal Scale and the Questionnaire of Smoking Urges, graph the before and after scores in their workbook.**
13. Un-pause the audio recording and continue the intervention by going over the participant's before and after scores for the Minnesota Nicotine Withdrawal Scale and Questionnaire of Smoking Urges.
14. Go over the Tobacco Use and NRT Use calendars.
15. Provide them with the copies of the calendars (in their folder) to keep in their pocket/wallet for use when they do not have their manual with them.
16. After the therapy, ask the participant if they have any questions. If they do not, tell them you are ending the recording.
17. Schedule the next appointment for the following week (preferably the same day of the week and the same morning time). **Once you have it scheduled, make sure the appointment is placed in the [name] Lab Google Calendar.**
18. Instruct the participant to **bring the calendars and workbook back so they can be reviewed next session.**
19. Give the participant 6 patches. The 6 patches and the patch they are currently wearing (total of 7) will last through to the next appointment.
20. Give the participant the box with the inhaler and cartridges. The inhaler cartridges will last through to the next appointment. **Be sure to emphasize they are not to use the inhaler on the morning of the next appointment.**
21. **Have the participant sign for the medication in the medication sign-out log.**
22. Mark in the Medication Inventory Excel sheet how many of the patches and inhaler boxes you have given out so that we maintain a running total of prescriptions we have on hand.
23. Remind the participant of the instructions on how to use the patches and inhaler and let them know they can reference their workbook if they forget. Give the participant the instructions sheet.
24. Compensate the participant on their Greenphire ClinCard.
25. Give the participant an appointment card. **Be sure to remind the participant to try and refrain from smoking the night before the appointment and not to use a inhaler on the morning of the appointment. Also, remind them to bring all used and unused patches, patch packets, and inhaler cartridges back to the next appointment.**
26. Upload the session recording to Box.com (MOP, pg. 14) and complete the Audio Recording Length form in REDCap.

